9.5. Analyses for the Data Monitoring Committee

Not applicable.

9.6. Interim Analysis

In Part 2, the Simon 2-stage design will be applied. During Stage 1, 9 evaluable subjects treated at the recommended dose and schedule will be enrolled, and if no responses are observed, then the cohort will be discontinued. The probability of early termination for Stage 1 is summarized in Table 18. If at least 1 response is observed, then 8 additional evaluable subjects will be enrolled (Stage 2).

Table 18: Probability of Early Termination of Stage 1 for Simon 2-Stage Design

True Response Rate	Probability of Early Termination at Stage 1
15%	23.2%
20%	13.4%
25%	7.5%
30%	4.0%
35%	2.1%

10. ETHICAL CONSIDERATIONS AND ADMINISTRATIVE PROCEDURES

10.1. Investigator Responsibilities

This study will be performed in accordance with ethical principles that originate in the Declaration of Helsinki and conducted in adherence to the study Protocol; GCPs as defined in Title 21 of the US Code of Federal Regulations (CFR) Parts 11, 50, 54, 56, and 312; ICH E6 GCP consolidated guidelines; and local regulatory requirements as applicable to the study locations.

The investigator will be responsible for:

- Permitting study-related monitoring, sponsor audits, IRB/IEC review, and regulatory inspections by providing direct access to source data and other relevant clinical study documents.
 - Monitoring: Qualified representatives of the sponsor or its designee, study monitors, will monitor the study according to a predetermined plan. The investigator must allow the study monitors to review any study materials and subject records at each monitoring visit.
 - Auditing: Qualified representatives of the sponsor or its designee may audit the clinical study site and study data to evaluate compliance with the Protocol, applicable local clinical study regulations, and overall study conduct. The investigator must allow the auditors to review original source records and study documentation for all subjects.
 - Regulatory inspection: Regulatory authorities may conduct an inspection of the study and the site at any time during the development of an investigational product. The investigator and staff are expected to cooperate with the inspectors and allow access to all source documents supporting the eCRFs and other study-related documents. The investigator must immediately notify the sponsor when contacted by any regulatory authority for the purposes of conducting an inspection.
- Obtaining informed consent and ensuring that the study subjects' questions have been answered and the subjects fully understand study procedures:
 - Informed consent must be obtained before any study-related procedures are conducted, unless otherwise specified by the Protocol.
 - Informed consent must be obtained using the IRB/IEC-approved version in a language that is native and understandable to the subject. A template will be provided by the sponsor or its designee. The sponsor or its designee must review and acknowledge the site-specific changes to the ICF template. The ICF must include a statement that the sponsor or its designee and regulatory authorities have direct access to subject records.

- Obtaining approval from the IRB/IEC before the start of the study and for any changes to the clinical study Protocol, important Protocol deviations, routine updates, and safety information in accordance with institutional requirements and local law.
 - The investigator is responsible for ensuring that the safety reports provided by the sponsor are reviewed and processed in accordance with regulatory requirements and with the policies and procedures established by the IRB/IEC.
- Adhering to the Protocol as described in this document and agreeing that changes to the Protocol procedures, with the exception of medical emergencies, must be discussed and approved, first, by the sponsor or its designee and, second, by the IRB/IEC. Each investigator is responsible for enrolling subjects who have met the specified eligibility criteria.
- Retaining records in accordance with all local, national, and regulatory laws, but for a minimum period of at least 2 years after the last marketing application approval in an ICH region and until there are no pending or contemplated marketing applications in an ICH region, or if not approved, 2 years after the termination of the test article for investigation to ensure the availability of study documentation should it become necessary for the sponsor or a regulatory authority to review.
 - The investigator must not destroy any records associated with the study without receiving approval from the sponsor. The investigator must notify the sponsor or its designee in the event of accidental loss or destruction of any study records. If the investigator leaves the institution where the study was conducted, the sponsor or its designee must be contacted to arrange alternative record storage options.
 - All eCRF data entered by the site (including audit trail), as well as computer hardware and software (for accessing the data), will be maintained or made available at the site in compliance with applicable record retention regulations. The sponsor will retain the original eCRF data and audit trail.

10.2. Accountability, Handling, and Disposal of Study Drug

The investigator is responsible for drug accountability at the study site; however, some of the drug accountability duties may be assigned to an appropriate pharmacist or other designee. Inventory and accountability records must be maintained and readily available for inspection by the study monitor and are open to inspection at any time by any applicable regulatory authorities.

The investigator or designee must maintain records that document:

- Delivery of study drug to the study site.
- Inventory of study drug at the site.
- Subject use of the study drug including pill or unit counts from each supply dispensed.
- Return of study drug to the investigator or designee by subjects.

The investigational product must be used only in accordance with the Protocol. The investigator will also maintain records adequately documenting that the subjects were provided the specified

study drug. These records should include dates, quantities, and any available batch or serial numbers or unique code numbers assigned to the investigational product and study subjects.

Completed accountability records will be archived by the site. The investigator or designee will be expected to collect and retain all used, unused, and partially used containers of study drug until verified by the study monitor (unless otherwise agreed to by the sponsor). At the conclusion of the study, the investigator or designee will oversee shipment of any remaining study drug back to the sponsor or its designee for destruction according to institutional standard operating procedures. If local procedures mandate on-site destruction of investigational supply, the site should (where local procedures allow) maintain the investigational supply until the study monitor inspects the accountability records in order to evaluate compliance and accuracy of accountability by the investigative site. At sites where the study drug is destroyed before monitor inspection, the monitors rely on documentation of destruction per the site SOP.

10.3. Data Management

Data management will be performed in a validated database via an Electronic Data Capture (EDC) system. All data entry, verification, and validation will be performed in accordance with the current standard operating procedures of the Data Management Department at the sponsor or its designee. The database will be authorized for lock once all defined procedures are completed.

The investigator will be provided with access to an EDC system so that an eCRF can be completed for each subject. Entries made in the eCRF must be verifiable against source documents; if updates to the database are not possible, any discrepancies should be explained and documented. The investigator will be responsible for reviewing all data and eCRF entries, and will sign and date the designated forms in each subject's eCRF, verifying that the information is true and correct. The investigator is responsible for the review and approval of all query responses.

Protocol deviations will be identified and recorded in the Protocol Deviation form of the eCRF. The study monitor will reference the Monitoring Plan in order to ensure that each issue identified is appropriately documented, reported, and resolved in a timely manner in accordance with the plan's requirements.

10.4. Data Privacy and Confidentiality of Study Records

The investigator and the sponsor or its designee must adhere to applicable data privacy laws and regulations. The investigator and the sponsor or their designees are responsible for ensuring that sensitive information is handled in accordance with local requirements (eg, HIPAA). Appropriate consent and authorizations for use and disclosure and/or transfer (if applicable) of protected information must be obtained.

Subject names will not be supplied to the sponsor or its designee, if applicable. Only the subject number and subject's initials (subject's initials will only be recorded if allowable by local regulations) will be recorded in the eCRF, where permitted; if the subject's name appears on any other document (eg, laboratory report), it must be obliterated on the copy of the document to be supplied to the sponsor or its designee. Study findings stored on a computer will be stored in accordance with local data protection laws. The subjects will be informed that representatives of the sponsor or its designee, IRB or IEC, or regulatory authorities may inspect their medical

records to verify the information collected, and that all personal information made available for inspection will be handled in strictest confidence and in accordance with local data protection laws.

10.5. Financial Disclosure

Before study initiation, all clinical investigators participating in clinical studies subject to FDA Regulation Title 21 CFR Part 54 – Financial Disclosure by Clinical Investigators (ie, "covered studies") are required to submit a completed Clinical Investigator Financial Disclosure form that sufficiently details any financial interests and arrangements that apply. For the purpose of this regulation, "clinical investigator" is defined as any investigator or subinvestigator who is directly involved in the treatment or evaluation of research subjects, including the spouse and each dependent child of the clinical investigator or subinvestigator. These requirements apply to both US and foreign clinical investigators conducting covered clinical studies.

Any new clinical investigators added to the covered clinical study during its conduct must also submit a completed Investigator Financial Disclosure Form. During a covered clinical study, any changes to the financial information previously reported by a clinical investigator must be reported to the sponsor or its designee. At the conclusion of the covered clinical study, the clinical investigators will be reminded of their obligations. In the event that the clinical investigator is not reminded, they nevertheless will remain obligated to report to the sponsor or its designee any changes to the financial information previously reported, as well as any changes in their financial information for a period of 1 year after completion of the covered clinical study.

10.6. Publication Policy

By signing the study Protocol, the investigator and his or her institution agree that the results of the study may be used by the sponsor, Incyte Europe Sàrl (Incyte), for the purposes of national and international registration, publication, and information for medical and pharmaceutical professionals. Study results will be published in accordance with applicable local and national regulations. If necessary, the authorities will be notified of the investigator's name, address, qualifications, and extent of involvement. The terms regarding the publication of study results are contained in the agreement signed with the sponsor or its designee. A signed agreement will be retained by the sponsor or its designee.

APPENDIX A. INFORMATION REGARDING EFFECTIVENESS OF CONTRACEPTIVE METHODS

For Subjects Participating in the Study:

The following methods that can achieve a failure rate of less than 1% per year when used consistently and correctly are considered as highly effective birth control methods.

Such methods include:

- Combined (estrogen and progestogen containing) hormonal contraception associated with inhibition of ovulation¹
 - oral
 - intravaginal
 - transdermal
- Progestogen-only hormonal contraception associated with inhibition of ovulation¹
 - oral
 - injectable
 - implantable²
- Intrauterine device (IUD)²
- Intrauterine hormone-releasing system (IUS)²
- Bilateral tubal occlusion²
- Vasectomised partner^{2,3}
- Sexual abstinence⁴

¹ Hormonal contraception may be susceptible to interaction with the IMP, which may reduce the efficacy of the contraception method.

² Contraception methods that in the context of this guidance are considered to have low user dependency.

³ Vasectomised partner is a highly effective method provided of avoiding pregnancy that partner is the sole sexual partner of the WOCBP trial participant and that the vasectomised partner has received medical assessment of the surgical success.

⁴ In the context of this guidance, sexual abstinence is considered a highly effective method only if defined as refraining from heterosexual intercourse during the entire period of risk associated with the study treatments. The reliability of sexual abstinence needs to be evaluated in relation to the duration of the clinical trial and the preferred and usual lifestyle of the subject.

Source: [CTFG 2014](#).

APPENDIX B. PROCEDURES AND SUPPORTIVE CARE GUIDELINES FOR SUBJECTS EXHIBITING IMMUNE-RELATED ADVERSE EVENTS

irAE	Supportive Care
Pneumonitis	
For Grade 2 (mild to moderate new symptoms):
 
 • Monitor symptoms daily and consider hospitalization. • Promptly start systemic steroids per institutional standard of care. • Consider adding prophylactic antibiotics for opportunistic infections in the case of prolonged steroid administration. • Reimaging as clinically indicated. • If no improvement within 3 to 5 days, additional work-up should be considered and prompt treatment with IV methylprednisolone should be started. • If still no improvement within 3 to 5 days despite IV methylprednisone, consider starting immunosuppressive therapy (eg, infliximab), after discussing with the medical monitor. 
Caution: Important to rule out sepsis and refer to infliximab label for general guidance before using infliximab.
 
 • Once improving, gradually taper steroids over ≥ 4 weeks and consider prophylactic antibiotics, antifungal, or anti-PCP treatment (refer to current NCCN Guidelines for treatment of cancer-related infections (Category 2B recommendation)). • Consider pulmonary and infectious disease consult. 
For Grade 3 or 4 (severe or new symptoms, new/worsening hypoxia, life threatening):
 
 • Promptly initiate empiric IV methylprednisolone or equivalent. • Carefully monitor subject, and institute medical intervention as appropriate for the management of symptoms. Consider obtaining pulmonary and infectious disease consult. • If no improvement within 3-5 days, additional work-up should be considered and prompt treatment with additional immunosuppressive therapy (eg, infliximab), after discussing with the medical monitor. 
Caution: Rule out sepsis and refer to infliximab label for general guidance before using infliximab.
 
 • Once improving, gradually taper steroids over ≥ 4 weeks and consider prophylactic antibiotics, antifungals, and in particular, anti-PCP treatment (refer to current NCCN Guidelines for treatment of cancer-related infections (Category 2B recommendation)).

irAE	Supportive Care
Diarrhea/Colitis	
Note: Subjects should be carefully monitored for signs and symptoms of enterocolitis (such as diarrhea, abdominal pain, blood or mucus in stool, with or without fever) and of bowel perforation (such as peritoneal signs and ileus).
 
For Grade 2 (mild to moderate new symptoms):
 
 • Consider symptomatic treatment, including hydration, electrolyte replacement, dietary changes (eg, American Dietetic Association colitis diet), and loperamide and/or budesonide. • Promptly start systemic steroids per institutional standard of care. • If event is not responsive within 3 to 5 days or worsens, gastrointestinal (GI) consult should be obtained for consideration of further work-up, and prompt treatment with IV methylprednisolone started. • If still no improvement within 3 to 5 days, consider starting immunosuppressives (eg, infliximab) after discussing with the medical monitor. 
Caution: Important to rule out bowel perforation and refer to infliximab label for general guidance before using infliximab.
 
 • Consult medical monitor if no resolution to \leq Grade 1 in 3 to 4 days. • Once improving, gradually taper steroids over \geq 4 weeks and consider prophylactic antibiotics, antifungals, and anti-PCP treatment (refer to current NCCN Guidelines for treatment of cancer-related infections [Category 2B recommendation]). 
For Grade 3 or 4 (severe or new symptoms, new/worsening hypoxia, life threatening):
 
 • Treatment with systemic corticosteroids should be initiated per institutional standard of care. • Manage symptoms and consider GI consult for further work-up as appropriate. • If still no improvement within 3 to 5 days, consider starting immunosuppressives (eg, infliximab), after discussing with the medical monitor. 
Caution: Ensure GI consult to rule out bowel perforation and refer to infliximab label for general guidance before using infliximab.
 
 • Once improving, gradually taper steroids over \geq 4 weeks and consider prophylactic antibiotics, antifungals, and anti-PCP treatment (refer to current NCCN Guidelines for treatment of cancer-related infections [Category 2B recommendation]).

irAE	Supportive Care
Hepatitis	
For Grade 2 (mild to moderate new symptoms):
 
 • Observe subject with regular and frequent checking of liver chemistries until improving or resolved. • Rule out non-irAE etiologies. • If event is persistent (> 3-5 days) or worsens, consider starting systemic steroids per institutional standard of care. • If still no improvement within 3 to 5 days, consider additional work-up and prompt treatment with IV methylprednisolone. • If still no improvement within 3 to 5 days, consider starting immunosuppressives (eg, mycophenolate mofetil), after discussing with the medical monitor. • Infliximab should NOT be used. • Once improving, gradually taper steroids over ≥ 4 weeks and consider prophylactic antibiotics, antifungals, and anti-PCP treatment (refer to current NCCN Guidelines for treatment of cancer-related infections [Category 2B recommendation]). 
For Grade 3 or 4 (severe or new symptoms, new/worsening hypoxia, life threatening):
 
 • Promptly initiate empiric IV methylprednisolone or equivalent. • If still no improvement within 3 to 5 days, consider starting treatment with immunosuppressive therapy (eg, mycophenolate mofetil), after discussing with the medical monitor. • Infliximab should NOT be used. • Consider hepatology consult for additional work-up, as appropriate. • Once improving, gradually taper steroids over ≥ 4 weeks and consider prophylactic antibiotics, antifungals, and anti-PCP treatment (refer to current NCCN Guidelines for treatment of cancer-related infections [Category 2B recommendation]).

irAE	Supportive Care
Dermatitis	
Note: Monitor subjects for signs and symptoms of dermatitis such as rash and pruritus. Unless an alternate etiology has been identified, signs or symptoms of dermatitis should be considered immune-mediated. If there is any bullous formation, the medical monitor should be contacted, and the study drug should be discontinued.
 
For Grade 2 (mild to moderate new symptoms):
 
 • Consider dermatology consult. • Consider symptomatic treatment per institutional standard of care. • Consider moderate-strength topical steroid. • If no improvement of rash/skin lesions occurs within 3 to 5 days or is worsening despite symptomatic treatment and/or use of moderate strength topical steroid, discuss with medical monitor and promptly start systemic steroids. 
For Grade 3 or 4 (severe or new symptoms, new/worsening hypoxia, life threatening):
 
 • Consider dermatology consult. • Promptly initiate empiric IV methylprednisolone or equivalent. • Carefully monitor subject, and institute medical intervention as appropriate for the management of symptoms. • Consider hospitalization. • Once improving, gradually taper steroids over ≥ 4 weeks and consider prophylactic antibiotics, antifungals, and anti-PCP treatment (refer to current NCCN Guidelines for treatment of cancer-related infections [Category 2B recommendation]). • Discuss with medical monitor.
Renal Failure or Nephritis	
Note: Subjects should be monitored for signs and symptoms that may be related to changes in renal function. Subjects should be thoroughly evaluated to rule out any alternative etiology. Steroids should be considered in the absence of clear alternative etiology even for low-grade events (Grade 2) in order to prevent potential progression to higher grade event.
 
For Grades 2 to 4:
 
 • Carefully monitor subject, and institute medical intervention as appropriate for the management of symptoms. Consider consult with nephrologist, if clinically indicated. • If event is persistent (> 3-5 days) or worsens, promptly start systemic steroids per institutional standard of care. • If event is not responsive within 3-5 days or worsens despite steroids, additional work-up should be considered, and prompt treatment with IV methylprednisolone started. • Once improving, gradually taper steroids over ≥ 4 weeks and consider prophylactic antibiotics, antifungals, and anti-PCP treatment (refer to current NCCN Guidelines for treatment of cancer-related infections [Category 2B recommendation]).

irAE	Supportive Care
Endocrinopathies	
Note: Subjects should be monitored for clinical signs and symptoms of hypophysitis, adrenal insufficiency (including adrenal crisis), and hyper- or hypothyroidism. Subjects may present with fatigue, headache, mental status changes, abdominal pain, unusual bowel habits, and hypotension, or report nonspecific symptoms which may resemble other causes such as brain metastasis or underlying disease. Unless an alternate etiology has been identified, signs or symptoms of endocrinopathies should be considered immune-mediated.
 
For Grade 2 (mild to moderate new symptoms):
 
 • In hypophysitis, treat with systemic corticosteroids, per institutional standard of care. When symptoms improve to Grade 1 or less, steroid taper should be started and continued over no less than 4 weeks. Replacement of appropriate hormones may be required as the steroid dose is tapered. 
Note: These suggested supportive care measures also apply to Grade 3 hypophysitis
 
 • In hyperthyroidism, nonselective beta-blockers (eg, propranolol) are suggested as initial therapy. • In hypothyroidism, thyroid hormone replacement therapy, with levothyroxine or liothyronine, is indicated per standard of care. 
Note: Isolated hypothyroidism may be treated with replacement therapy without treatment interruption and without corticosteroids.
 
 • Evaluate endocrine function and, as clinically indicated, consider pituitary scan. • For subjects with abnormal endocrine work-up, except for those with isolated hypothyroidism, consider short-term, high-dose corticosteroids (eg, methylprednisolone or IV equivalent) and initiate appropriate hormone replacement therapy. • For subjects with normal endocrine work-up (labs or MRI), repeat labs/MRI as clinically indicated. 
For Grade 3 or 4 (severe or new symptoms, new/worsening hypoxia, life threatening):
 
 • Hypothyroidism may be treated with replacement therapy without treatment interruption and without corticosteroids. • In hyperthyroidism, treat with an initial dose of IV corticosteroid followed by oral corticosteroids. Consider initiation of systemic corticosteroids at a dose of 1-2 mg/kg per day of prednisone or equivalent, and initiate appropriate hormone replacement therapy. Once improving, gradually taper immunosuppressive steroids over ≥ 4 weeks. • In hypophysitis, treat with an initial dose of IV corticosteroids followed by oral corticosteroids. When symptoms improve to Grade 1 or less, steroid taper should be started and continued over no less than 4 weeks. Replacement of appropriate hormones may be required as the steroid dose is tapered. • For adrenal crisis, severe dehydration, hypotension, or shock: immediately initiate intravenous corticosteroids with mineralocorticoid activity. • Consult endocrinologist. • Consult medical monitor.

irAE	Supportive Care
Neuropathies	
Note: Monitor subjects for symptoms of motor or sensory neuropathy such as unilateral or bilateral weakness, sensory alterations, or paresthesia.
 
For Grade 2 (mild to moderate new symptoms):
 
• Consider systemic corticosteroids per institutional standard of care in addition to appropriate symptomatic treatment.• If no improvement within 3-5 days, consider additional work-up and consider treating with additional immunosuppressive therapy (eg, IV IgG), after discussing with the medical monitor. 
For Grade 3 or 4 (severe or new symptoms, new/worsening hypoxia, life threatening):
 
• Consider initiation of systemic corticosteroids (IV administration should be strongly considered) for severe neuropathies.• Institute medical intervention as appropriate for management of severe neuropathy.• If no improvement within 3-5 days despite IV corticosteroids, consider additional workup and consider treating with additional immunosuppressants (eg, IV IgG) after discussing with the medical monitor.• Once stable, gradually taper steroids over ≥ 4 weeks.

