5.4.6. Criteria and Procedures for Dose Interruptions and Adjustments of Study Drug

Treatment with study drug may be delayed to allow for resolution of toxicity. Subjects may resume treatment if no medical condition or other circumstance exists that, in the opinion of the investigator, would make the subject unsuitable for further participation in the study. For toxicities that occur outside of the 28-day DLT period, the treating investigator should contact the medical monitor to discuss the case of any subject whose treatment has been delayed for more than 4 weeks (28 days) before restarting treatment with study drug.

Instructions for dose modifications and interruptions are outlined in [Table 4](#). Individual decisions regarding dose interruptions and reductions should be made using appropriate clinical judgment in consultation with the medical monitor, taking into account relatedness of the AE to the study drug and the subject's underlying condition. Adverse events that have a clear alternative explanation, or transient (≤ 72 hours) abnormal laboratory values without associated clinically significant signs or symptoms may be exempt from dose-reduction rules. Dose interruptions are permitted in the case of medical/surgical events or logistical reasons not related to study therapy (eg, elective surgery, unrelated medical events, subject vacation, and/or

holidays). Subjects should be placed back on study therapy within 4 weeks (28 days) of the scheduled interruption, unless otherwise discussed with the sponsor. The reason for interruption should be documented in the subject's study record.

Table 4: Rules for Interruption and Restarting of Study Drug

CTCAE Grade or Severity	Timing for Restarting Treatment	Dose Level for Restarting Treatment	Treatment Discontinuation
1-2 (mild-moderate)	Continue treatment at the discretion of the investigator.	N/A	N/A
3 (severe)	Toxicity resolves to Grade 0-1.	Reduce by 1 dose level. ^a	Toxicity does not resolve within 4 weeks (28 days) of last dose, except by approval of the medical monitor. OR Second occurrence of previously resolved Grade 3 AE.
4 (life-threatening)	Permanently discontinue.	N/A	Permanently discontinue.

Note: Permanently discontinue for any severe or Grade 3 AE that recurs or any life-threatening event.

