^a No more than 2 dose reductions of study drug are permitted, or 1 dose reduction of study drug if the starting dose is 0.03 mg/kg (see Table 2). Subjects should be permanently discontinued from study drug if they have AEs requiring more than 2 dose reductions of study drug.

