5.4.9. Criteria for Permanent Discontinuation of Study Drug

The occurrence of an unacceptable toxicity not caused by the underlying malignancy will be presumed to be related to study drug and will require that the study drug be permanently discontinued. Unacceptable toxicity is defined as follows:

- Grade 4 or life-threatening AEs (see [Table 4](#) and [Table 6](#)).
- \geq Grade 2 ocular irAE.
- Occurrence of an AE that is related to treatment with the study drug that, in the judgment of the investigator or the sponsor's medical monitor, compromises the subject's ability to continue study-specific procedures, or is considered to not be in the subject's best interest.
- An AE requiring more than 2 dose reductions of study drug, or more than 1 dose reduction of study drug if the starting dose is 0.03 mg/kg (see [Table 2](#)).
- Persistent AE requiring a delay of study drug beyond 4 weeks (28 days), unless the delay has been approved by the sponsor.

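### Appendix B allows Grade 4 hypothyroidism to be treated without stopping study drug, against the mandatory discontinuation rule; at Grade 3 it departs more mildly from Tables 4 and 5

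*Protocol*

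**What the plan says.** Four parts of the protocol bear on dosing when a subject develops severe hypothyroidism.

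- **Appendix B, Endocrinopathies.** The list headed Grade 3 or 4, a heading that itself includes life-threatening events, opens by saying that "hypothyroidism may be treated with replacement therapy without treatment interruption and without corticosteroids". The list ends with an instruction to consult the medical monitor.
- **Section 5.4.6 and Table 4.** For a Grade 3 event, the condition for restarting is "Toxicity resolves to Grade 0-1" and the restart dose is "Reduce by 1 dose level". The Grade 4 row calls for permanent discontinuation, and the note below the table reads "Permanently discontinue for any severe or Grade 3 AE that recurs or any life-threatening event". The text above the table adds that "Individual decisions regarding dose interruptions and reductions should be made using appropriate clinical judgment in consultation with the medical monitor". Footnote a sets the limit: "No more than 2 dose reductions of study drug are permitted", or one if the starting dose was 0.03 mg/kg.
- **Sections 5.4.9 and 5.5.1.** Unacceptable toxicity not caused by the malignancy "will require that the study drug be permanently discontinued". The first item in its definition is "Grade 4 or life-threatening AEs". Section 5.5.1 then makes withdrawal from study drug compulsory for such subjects.
- **Section 5.4.7 and Table 5.** In the Grade 3-4 row, Table 5 tells sites to give corticosteroids. Both the section and the table's footnote send the reader to Appendix B for detail on specific immune-related events.

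**The concern.** A site managing a thyroid event is directed to Appendix B and finds a line that lets dosing continue at either grade. At Grade 4, a site relying on that line would go on dosing a subject who must be withdrawn under Section 5.5.1. At Grade 3, whether the subject continues at full dose or is held and reduced depends on which page the site reads. The second course uses up part of a small allowance of dose reductions. The stake is consistent, safe handling of individual subjects, not the trial's operating characteristics.

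**Working it through.** No figure in the plan needs reproducing here, so the check is to set the texts side by side by grade.

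| Grade of hypothyroidism | Appendix B | Table 4 and related sections | Table 5 | Result |
|---|---|---|---|---|
| 2 | No interruption, no corticosteroids (isolated hypothyroidism only) | Continue at investigator's discretion | Corticosteroids to be considered | Compatible |
| 3 | No interruption, no corticosteroids | Hold to Grade 0-1, restart one level lower; judgment with the medical monitor allowed | Give corticosteroids | Different defaults, softened by judgment |
| 4 | No interruption, no corticosteroids | Permanent discontinuation (Table 4, Sections 5.4.9 and 5.5.1) | Give corticosteroids | Contradiction |

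**Is there an exception that reconciles Grade 4?** Three places could hold one.

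1. Section 5.4.9 excludes only toxicity caused by the underlying malignancy. Appendix B tells sites to treat endocrinopathies as immune-mediated unless another cause is found, so that exclusion would not ordinarily apply.
2. Section 5.4.6 allows exemption from the dose-reduction rules for events with another evident cause and for brief, symptom-free laboratory changes. It does not mention hypothyroidism or hormone replacement.
3. The clinical-judgment sentence in Section 5.4.6 concerns interruptions and reductions. It does not waive permanent discontinuation.

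None of the three supplies an exception, and no sentence ranks Appendix B against the dosing rules.

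**How firm is the Grade 3 difference?** Table 4's default and the Appendix B line cannot both be followed to the letter. But the judgment sentence quoted above covers exactly this decision, and Appendix B also brings in the medical monitor. A site that continues dosing after that consultation is arguably within Section 5.4.6. The corticosteroid instructions in Table 5 and Appendix B still point in opposite directions.

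**What does a Grade 3 subject lose under Table 4?** One dose reduction. The allowance falls from 2 to 2 − 1 = 1, or from 1 to 1 − 1 = 0 if the starting dose was 0.03 mg/kg.

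**Does the choice change DLT counting?** No such effect is shown. Under Table 3, a nonhematologic toxicity of Grade 3 or higher in the 28-day window is already a DLT unless a listed exception applies, whichever dosing rule the site then follows.

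**The case against.** The best reply is that the protocol already shows which text controls dosing. Section 5.4.6 names Table 4 as the place for modification and interruption instructions, Section 5.4.9 refers to Tables 4 and 6, and Section 5.5.1 refers back to Section 5.4. None of them cites Appendix B, which is described as supportive-care guidance. A permissive line should yield to a mandatory one, and medical monitor consultation gives a further safeguard. Much of this stands: a careful reader would apply the Grade 4 stop. It does not remove the fault, because the Appendix B line speaks expressly about interrupting treatment, sits under a Grade 4 heading, and is where sites are sent for detail.

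A reader might also infer more than the documents support:

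- *That three independent texts contradict Appendix B at Grade 4.* Table 4, Section 5.4.9 and Section 5.5.1 cross-refer and form one rule.
- *That Table 5 adds a third Grade 3 default, a permanent stop.* Its stop is limited to clinically significant or severe immune-related events within a row already labelled Grade 3-4. It can be read as a matter of judgment, so it does not clearly require stopping for every Grade 3 event.
- *That frequent thyroid testing, or the eligibility of subjects with existing thyroid disease, shows the size of the problem.* A test schedule is not an event rate. Laboratory changes are adverse events only under the conditions in Section 8.1.1, and conditions present at consent are medical history.
- *That a general precedence sentence is needed, making the stricter text govern.* If Table 5's stop is read as covering all Grade 3 events, that sentence would replace Table 4's hold-and-reduce with a permanent stop for every other Grade 3 immune-related event. That is a clinical change, not a clarification.

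**Conclusion.** The point holds. At Grade 4 the Appendix B allowance contradicts a mandatory stopping rule that has no endocrine exception, and the text should be corrected. At Grade 3 there is a real but softer mismatch with Table 4 on holding and reducing, and with Table 5 on corticosteroids. Clinical judgment and medical monitor consultation already leave room for the Appendix B course.

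The reach is limited to subjects with Grade 3 or 4 hypothyroidism; the documents give no rate and none is assumed. The conclusion rests on reading the Appendix B heading as it stands, covering both grades. It is a matter of safety conduct: no effect on sample size, DLT counts, escalation decisions or efficacy analysis is claimed.

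**What to change.** 1. **Appendix B, Endocrinopathies, Grade 3 or 4.** Put the words *Grade 3* at the start of the hypothyroidism bullet, leave the rest of it as it is, and add: *Grade 4: permanently discontinue study drug (Table 4, Section 5.4.9).*
2. **Table 4, Grade 3 row, and Table 5, Grade 3-4 row.** Add to each: *Exception: for Grade 3 hypothyroidism managed with hormone replacement, study drug may continue without interruption, dose reduction or corticosteroids, in consultation with the medical monitor.* This carries the existing Appendix B allowance into the dosing text and settles the corticosteroid mismatch.

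The exception leaves untouched the Table 4 stop for a Grade 3 event that recurs; if the sponsor wants that relaxed for replaced hypothyroidism, it must say so. No general precedence sentence is proposed.

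The cost is one edited bullet and one exception placed in two tables at the next amendment. Sample size, visits and analyses do not change.
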